2.3 Safety objectives

To compare the safety of naloxegol (with placebo) in critically ill adults initiated on scheduled IV opioids for each of the following outcomes:

During the period from time of study enrollment (i.e. randomization) to ICU discharge, death or 10 days of study drug administration (whatever comes first):

- a. Diarrhea:
 - a. Daily presence
 - b. Time from study drug initiation to first episode of diarrhea

Note: Diarrhea is defined where \geq 3 loose or watery stools 24 hour period as defined by a Bliss stool scale score of 3 (loose and unformed stool) or 4 (liquid stool)].
- b. Days without a diaper or rectal tube
- c. Days without a rectal tube
- d. Daily difference in the pre-dose and post-dose Clinical Opioid Withdrawal Scale (COWS) score (as evaluated by the bedside nurse before and 2 hours after the administration of the daily study drug dose).

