Measurement of bladder pressure in subjects with a foley catheter in place for a clinical reason (to estimate abdominal pressure) q8h		√	√	√	√	√	√	√	√	√	√	√	
Investigative team													
Requirement for mechanical ventilation	√	√	√	√	√	√	√	√	√	√	√	√	
SOFA score calculation (daily)		√	√	√	√	√	√	√	√	√	√	√	
Occurrence of lower GI tract paralysis requiring a GI or surgical consult		√	√	√	√	√	√	√	√	√	√	√	
Safety outcomes													
Monitoring that is a routine part of care at Tufts MC													
Bedside nurse													
Presence of diarrhea	√	√	√	√	√	√	√	√	√	√	√	√	
Investigative team													
Presence of a diaper or rectal tube		√	√	√	√	√	√	√	√	√	√	√	
Monitoring that is not a routine part of care at Tufts MC													
Bedside nurse													
Characterization of diarrhea using the Bristol Scale		√	√	√	√	√	√	√	√	√	√	√	
Evaluation for opioid withdrawal using the COWS scale before and 2 hours after each daily study dose		√	√	√	√	√	√	√	√	√	√	√	

Additional assessments not included in table:

1. Baseline demographics [age, gender, APACHE II score, Charlson comorbidity scale score, primary reason for ICU admission (based on APACHE III criteria)], baseline comorbidities potentially associated with an increased risk for lower gastrointestinal tract paralysis, treatments

Drug Substance: Movantik
Study Number: ESR-15-11000
Tufts IRB #12043
Version: Protocol version #19
Date: September 10, 2018

received at the time of ICU admission or administered after ICU admission that might influence SBM frequency and/or lower gastrointestinal tract paralysis incidence, and primary reason(s) for scheduled opioid initiation.

2. Evaluation for adverse events

Impact of Level of Sedation on Patient Assessments: Patients admitted to the Medical ICU at Tufts MC are generally maintained in an awake or lightly sedated state. For a patient who may require a short period of deeper sedation all of the following assessments above will be able to be still evaluated/collected **except:** COWS

Drug Substance: Movantik
Study Number: ESR-15-11000
Tufts IRB #12043
Version: Protocol version #19
Date: September 10, 2018

3.2 Rationale for study design, doses and control groups.

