5.5.2 Doses and treatment regiments

Treatment arm:

Naloxegol 25 mg daily [administered orally (or enterally)]

A lower dose of naloxegol (12.5mg mg daily) will be administered in the following two situations:

- a. A patient who is receiving a moderate CYP3A4 inhibitor that includes diltiazem, erythromycin, fluconazole, or verapamil (at any dose)
- b. A patient with a calculated creatinine clearance (using the modified MDRD approach) ≤ 60 ml/min

This based on the following information included in the Movantik package insert:

Drug Substance: Movantik
 Study Number: ESR-15-11000
 Tufts IRB #12043
 Version: Protocol version #19
 Date: September 10, 2018

- 1 **Under drug interactions: The concomitant use of naloxegol and a moderate CYP3A4 inhibitor may increase naloxegol serum concentrations.** If use cannot be avoided, the dose of naloxegol should be reduced to 12.5mg daily. The investigators are hesitant to exclude all medical ICU patients receiving a moderate CYP3A4 inhibitors from the study given that the list of medications in this list is long and many are used with a high prevalence in the ICU (e.g. diltiazem, erythromycin, fluconazole, or verapamil). With a 12.5 mg naloxegol tablet (and matching placebo) available from AstraZeneca, it will be feasible to administer the lower 12.5 mg daily naloxegol dose to subjects with this potential interaction without compromise the rigor or blinding of the study.
- 2 **Under dosage and administration: The starting dose for patients with a creatinine clearance ≤ 60 ml/min is 12.5 mg daily.** This dose recommendation is based on the fact that some patients with a creatine clearance ≤ 60 ml/min who were exposed to naloxegol 25mg daily were shown to exhibit markedly higher systemic exposure to naloxegol compared to subjects with normal renal function. Given that naloxegol is metabolized through the cytochrome P450 system of the liver, the reason for these high levels is not understood. The investigators are hesitant to exclude all medical ICU patients with a calculated creatinine clearance ≤ 60 mL/min given that this population represents more than 50% of the medical ICU population. With a 12.5 mg naloxegol tablet (and matching placebo) available from AstraZeneca, it will be feasible to administer the lower 12.5 mg daily naloxegol dose to subjects with renal dysfunction without compromise the rigor or blinding of the study.

Note:

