6.4 Safety

6.4.1 List of each safety variable

As outlined in Table 1:

Presence of diarrhea
 Presence of diaper
 Presence of rectal tube
 Difference in the pre-dose and post-dose Clinical Opioid Withdrawal Scale (COWS) score (as evaluated by the bedside nurse before and 2 hours after the administration of the daily study drug dose).

6.4.2 Definition for a serious adverse events and unanticipated problems:

Serious Adverse Event:

Events of a serious nature even if not related to the study (e.g. resulted in death, was life-threatening, resulted in hospitalization or prolongation of existing hospitalization, resulted in persistent or significant disability/incapacitation, may jeopardize the subject's health and may require medical or surgical intervention to prevent one of the other outcomes listed above).

Unanticipated Problem:

An event that meets all of the following criteria: 1) was unexpected; 2) was related or probably related to participation in the study, 3) may place subject(s) or others at greater risk of harm than previously recognized.

Please note that these can include:

- i. events that are identified in the ICF, but that are more severe and longer lasting than expected.
- iii events that were not expected to occur during the course of the study and that are not identified in the ICF(s).
- iv. any event about which the Principal Investigator is unsure, whether or not it meets the above criteria

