11.2 Calculation or derivation of safety variables

Please see table 1 and study objectives section

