Appendix 9. Daily Nursing Data Collection Form.

Subject ID: _____ Subject Initials: _____ ICU Room: _____ *Date (of day shift): _____ Study day# _____

*Note: this monitoring form goes from 07:00h to 06:59h the next day

Time of study drug administration : _____ h (note: should be around 0900h; if patient on tube feeds, please hold 1 hour before & after administration ; if patient is eating, administer 1 hour before or 2 hours after breakfast)

[Complete study drug administration instructions on next page]

Clinical Opioid Withdrawal Scale (COWS) Score to be completed 1 hour before and 2 hours after study drug administration (see next page)

Spontaneous Bowel Movements (from 0800h to 07:59h)	Time	Size (indicate small (S), medium (M) or large (L) (Use best judgment)	Bliss Stool Scale Score (see next page and on wall)	Comments
#1				
#2				
#3				
#4				
#5				
#6				
#7				
#8				

Does the patient have a urinary (foley) catheter in place for a clinical reason (s) Yes _____ No _____

Was the patient's ICU physician asked about whether the urinary (foley) catheter can be removed? Yes _____ No _____

Was the study laxative protocol utilized? Yes _____ No _____ If YES, which level? _____

Time frame	Day Shift (0700 – 14:59h)	Afternoon shift (15:00-22:59H)	Night shift (23:00-06:59h)
------------	---------------------------	--------------------------------	----------------------------

Drug Substance: Movantik
 Study Number: ESR-15-11000
 Tufts IRB #12043
 Version: Protocol version #19
 Date: September 10, 2018

Abdominal pressure score			
Time of evaluation			

For any questions regarding this study please page [name] or [name] at [name]

initials of investigational team member completing/verifying form _____ date _____

Clinical Opioid Withdrawal Scale (COWS) Score	1 hour before admin Time: _____	2 hours after admin Time: _____
Heart Rate: 0 = 80 bpm or below 1 = 81 to 100 bpm 2 = 101-120 bpm 4 = 121+ bpm		
Sweating over past ½ hour not accounted for by room temperature or patient activity: 0 = no chills or flushing 1 = patient reports chills or flushing 2 = flushed or observable moistness on face 3 = beads of sweat on brow or face 4 = sweat streaming off face		
Restlessness: 0 = able to sit or lie still 1 = patient reports difficulty sitting/lying still, but is able to do so 3 = frequent shifting or extraneous movements of legs/arms 5 = unable to sit/lie still for more than a few seconds		

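### The only defined withdrawal outcome is the same-day COWS difference, so from day 2 withdrawal already present before the dose, and steady or falling over the next three hours, contributes zero or less

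*Protocol*

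**What the plan says.** The safety objectives (Protocol 2.3) list the withdrawal outcome as "Daily difference in the pre-dose and post-dose Clinical Opioid Withdrawal Scale (COWS) score". The list of safety variables (6.4.1) repeats it: "Difference in the pre-dose and post-dose Clinical Opioid Withdrawal Scale (COWS) score". For derivation, Section 11.2 says only "Please see table 1 and study objectives section". Table 1 schedules "Evaluation for opioid withdrawal using the COWS scale before and 2 hours after each daily study dose", starting on treatment day 1.

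The daily nursing form (Appendix 9) fixes the times: "Clinical Opioid Withdrawal Scale (COWS) Score to be completed 1 hour before and 2 hours after study drug administration", with a dose that "should be around 0900h". The form records both total scores beside four severity bands (5-12 mild, 13-24 moderate, 25-36 moderately severe, above 36 severe). None of these bands enters an outcome.

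Section 12.2 of the SAP names no COWS analysis. Neither document defines a change from the first pre-dose score, a maximum, a threshold or a time to withdrawal. The note after Table 1 says COWS is the one assessment that cannot be made during deeper sedation.

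**The concern.** A within-day difference measures what happens in the hours around a dose. It is a sound measure of acute precipitated withdrawal. It does not measure whether a patient is in withdrawal, because each morning's score becomes the new reference. From day 2 that reference follows earlier study drug, so withdrawal already present is subtracted out.

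Section 1.4(f) names opioid withdrawal as a risk of the drug and lists COWS monitoring as a safeguard. The hypothesis in 1.3 includes the absence of safety concerns. Section 5.5.2 also expects renal function and interacting drugs to change during the stay, so day 1 need not represent later exposure. If the subtraction happens within each naloxegol patient, the placebo arm cannot restore the signal. The between-arm comparison could then look reassuring while absolute scores differed.

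**Working it through.** There is no stated figure to reproduce. The check is what the defined variable returns for given patterns of scores.

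**Timing.** With a dose at about 0900h, the scores fall at about 0800h and 1100h (Appendix 9).
- Time from the previous dose to the pre-dose score from day 2, with uninterrupted dosing: 24 − 1 = 23 hours. It is longer after a diarrhea hold (5.8.1, item 8).
- Window covered by the two scores: 1 + 2 = 3 hours. Unassessed until the next pre-dose score: 24 − 3 = 21 hours.
- Dosing lasts at most 10 days (5.8.1, item 4), so at most 10 − 1 = 9 of 10 differences have a pre-dose score that follows exposure.

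**Identity.** Let D_t = post_t − pre_t be the outcome on day t, and C_t = post_t − pre_1 the change from the day-1 pre-dose score. Then D_t = C_t − (pre_t − pre_1). Any elevation carried into the pre-dose score is removed in full, and D_t ≤ 0 whenever post_t ≤ pre_t, however high both scores are.

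**Illustration.** The following are assumptions, not figures from the documents: pre_1 = 3, a rise R of 10 points (range 5 to 15), and ten dosing days. The documents do not say how daily differences are combined; the ten-day mean is used here only as a summary.

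| Pattern | D_t, day 1 | D_t, days 2-10 | Mean D_t | Mean C_t |
|---|---|---|---|---|
| Onset within 2 h of dose 1, sustained | +10 | 0 | 10/10 = 1.0 (0.5 to 1.5) | 10 (5 to 15) |
| Onset more than 2 h after dose 1, sustained | 0 | 0 | 0 | 9 × 10/10 = 9.0 (4.5 to 13.5) |
| Delayed onset, high at each later pre-dose score, half resolved by 2 h post-dose | 0 | −5 | 9 × (−5)/10 = −4.5 (−2.25 to −6.75) | 9 × 5/10 = +4.5 (2.25 to 6.75) |
| Onset within 2 h of each dose, resolved before the next | +10 | +10 | 10 (5 to 15) | 10 (5 to 15) |

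The highest score is 3 + R = 13 (8 to 18) in every row. At R = 10 that is in the form's moderate band. The defined outcome represents only the last pattern fully. It shows the first on one day, misses the second, and gives the third the sign of an improvement.

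**Specificity of the lower band.** On the form, a pulse of 101-120 scores 2 and loose stool scores 2, giving 4, one point short of 5. A pulse above 120 scores 4, which with loose stool gives 6. A threshold of 5 can therefore be approached or passed without any other sign.

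**The case against.** The strongest reply has four parts.

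- **Some withdrawal is captured.** Day 1 has an untreated reference, so early onset registers once, and any further rise within 2 hours of a later dose scores positive. This stands. A reader might infer that sustained or delayed withdrawal always scores zero or improvement; that holds only when the score is steady or falling across the window.
- **Drug level is undocumented.** A reader might infer that later pre-dose scores are taken under active drug. The documents give no half-life, so they support only that these scores follow earlier exposure. The identity above does not depend on the residual level.
- **There are other routes to detection.** Adverse events are evaluated (note to Table 1), drug can be stopped for an attributable event (5.8.1), and the bedside form shows absolute totals. The DSMB reviews all subject data (12.3) and a closed report on safety by blinded group (Appendix 8). A reader might infer that persistent withdrawal would go unseen; these provisions do not support that. They do not, however, specify a COWS summary between arms that would show it.
- **Absolute scores are non-specific in the ICU.** Critical illness and opioid weaning raise them, and a within-day difference cancels slow drift. This is a good reason to keep the difference and to read absolute scores only between randomized arms.

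The protocol also describes withdrawal as very rare (1.4 f) and excludes strong CYP3A4 inhibitors. That lowers the expected frequency but does not change what the outcome measures.

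**Conclusion.** The point holds in a limited form. With up to 9 of 10 differences referenced to a post-exposure score, withdrawal that began more than 2 hours after a previous dose, or has persisted, contributes zero or less when it is steady or falling over the 3-hour window. No specified between-arm COWS summary would show it. This follows from the definition and the assessment times and needs no assumption about drug levels.

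The score sizes are illustrative. They show direction and possible scale, not an expected effect, and 9 of 10 is a maximum because 5.8.1 allows earlier stopping. A reader might go further and infer that the trial would wrongly declare the drug free of withdrawal. The documents set no rule that turns a mean difference near zero into such a conclusion, so that is not supported. The weakness lies in the outcome definition: the raw scores are collected, and the summaries should be specified before unblinding.

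**What to change.** Keep the within-day difference for acute effects. Add the following to 2.3(d) and the SAP, by arm, and by blinded group in the DSMB closed report:

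1. Each patient's maximum absolute COWS, and the proportion ever reaching the form's bands, using all pre- and post-dose scores. Use 13 or more as the main threshold and 5 or more as descriptive only. This needs no baseline score.
2. The change of each pre- and post-dose score from the day-1 pre-dose score, in patients who have one.
3. The number of COWS assessments missing because of deeper sedation, with missing day-1 pre-dose scores shown separately. Section 5.2.1 expects about two-thirds of potential subjects to be ventilated and receiving sedatives, so the loss could be material for item 2.

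State that absolute scores are to be read only as a comparison between arms.

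The cost is a few lines of text and one extra table, with no new assessments. Two limits remain: absolute scores partly reflect critical illness and opioid weaning, and withdrawal that starts and resolves in the roughly 21 hours between assessments would still not be seen.

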APPENDIX 1 Clinical Opiate Withdrawal Scale

For each item, circle the number that best describes the patient's signs or symptom. Rate on just the apparent relationship to opiate withdrawal. For example, if heart rate is increased because the patient was jogging just prior to assessment, the increase pulse rate would not add to the score.

Patient's Name: _____		Date and Time _____ / _____ / _____
Reason for this assessment: _____		
Resting Pulse Rate: _____ beats/minute Measured after patient is sitting or lying for one minute 0 pulse rate 80 or below 1 pulse rate 81-100 2 pulse rate 101-120 4 pulse rate greater than 120	GI Upset: over last 1/2 hour 0 no GI symptoms 1 stomach cramps 2 nausea or loose stool 3 vomiting or diarrhea 5 multiple episodes of diarrhea or vomiting	
Sweating: over past 1/2 hour not accounted for by room temperature or patient activity. 0 no report of chills or flushing 1 subjective report of chills or flushing 2 flushed or observable moistness on face 3 beads of sweat on brow or face 4 sweat streaming off face	Tremor: observation of outstretched hands 0 no tremor 1 tremor can be felt, but not observed 2 slight tremor observable 4 gross tremor or muscle twitching	
Restlessness: Observation during assessment 0 able to sit still 1 reports difficulty sitting still, but is able to do so 3 frequent shifting or extraneous movements of legs/arms 5 unable to sit still for more than a few seconds	Yawning: Observation during assessment 0 no yawning 1 yawning once or twice during assessment 2 yawning three or more times during assessment 4 yawning several times/minute	
Pupil size 0 pupils pinned or normal size for room light 1 pupils possibly larger than normal for room light 2 pupils moderately dilated 5 pupils so dilated that only the rim of the iris is visible	Anxiety or Irritability 0 none 1 patient reports increasing irritability or anxiousness 2 patient obviously irritable or anxious 4 patient so irritable or anxious that participation in the assessment is difficult	

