Bone or Joint aches If patient was having pain previously, only the additional component attributed to opiates withdrawal is scored 0 not present 1 mild diffuse discomfort 2 patient reports severe diffuse aching of joints/muscles 4 patient is rubbing joints or muscles and is unable to sit still because of discomfort	Gooseflesh skin 0 skin is smooth 3 piloerection of skin can be felt or hairs standing up on arms 5 prominent piloerection	
Runny nose or tearing Not accounted for by cold symptoms or allergies 0 not present 1 nasal stuffiness or unusually moist eyes 2 nose running or tearing 4 nose constantly running or tears streaming down cheeks	Total Score _____ The total score is the sum of all 11 items Initials of person completing assessment: _____	

Score: 5-12 = mild; 13-24 = moderate; 25-36 = moderately severe; more than 36 = severe withdrawal

This version may be copied and used clinically.

Journal of Psychoactive Drugs

Volume 35 (2), April - June 2003

Source: Wesson, D. R., & Ling, W. (2003). The Clinical Opiate Withdrawal Scale (COWS). *J Psychoactive Drugs*, 35(2), 253-9.

Drug Substance: Movantik
 Study Number: ESR-15-11000
 Tufts IRB #12043
 Version: Protocol version #19
 Date: September 10, 2018

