Pupil Size: 0 = pupils pinned or normal size for room light 1 = pupils possibly larger than normal for room light 2 = pupils moderately dilated 5 = pupils so dilated that only the rim of the iris is visible		
Bone or Joint Aches (if Patient was Having Pain Previously, only the Additional Component Attributed to Opiate Withdrawal Scale): 0 = not present 1 = mild diffuse discomfort 2 = patient reports severe diffuse aching of joints/muscles 4 = patient is rubbing joints or muscles and is unable to sit still because of discomfort		
Runny Nose or Tearing Not Accounted for by Cold Symptoms or Allergies: 0 = not present 1 = nasal stuffiness or unusually moist eyes 2 = nose is running or tearing 4 = nose constantly running or tears streaming down cheeks		
GI Upset: Over Last ½ Hour: 0 = no GI symptoms 1 = stomach cramps 2 = nausea or loose stool 3 = vomiting or diarrhea 5 = multiple episodes of vomiting or diarrhea		
Tremor Observation of Outstretched Hands:		

Drug Substance: Movantik
 Study Number: ESR-15-11000
 Tufts IRB #12043
 Version: Protocol version #19
 Date: September 10, 2018

0 = no tremor 2 = slight tremor observable	1 = tremor can be felt by patient, but not observed 4 = gross tremor or muscle twitching		
Yawning Observation During Assessment: 0 = no yawning/intubated 2 = yawning three or more times during assessment	1 = yawning once or twice during assessment 4 = yawning several times/minute		
Anxiety or Irritability: 0 = none 2 = patient obviously irritable/anxious	1 = patients reports increasing irritability or anxiousness 4 = patient so irritable or anxious that participation in the assessment is difficult		
Gooseflesh Skin: 0 = skin is smooth 5 = prominent piloerection	3 = piloerection of skin can be felt or hairs standing up on arms		
Total Score: 5-12 = Mild 13-24 = Moderate 25-36 = Moderately Severe More than 36 = Severe Withdrawal			

Study Drug Administration Instructions

If oral study drug medication is not possible (e.g. intubation) then the study drug should be administered via a gastric or enteral tube.

Tube feeds (if being administered) should be held for one hour and the feeding tube will be flushed with 30 mL of sterile water.

Crush the naloxegol (or matching placebo) tablet, mix in 60 mL of sterile water and draw up the contents (of the medication and sterile water) in a 60 mL oral syringe and administer via the gastric or enteral tube over 3-5 minutes.

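### The withdrawal safety outcome uses total COWS, whose GI item can move the pre/post difference by up to 5 of 48 points either way, so bowel effect and withdrawal are mixed

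*Protocol*

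**What the plan says.** Protocol section 2.3(d) lists as a safety outcome the "Daily difference in the pre-dose and post-dose Clinical Opioid Withdrawal Scale (COWS) score", rated by the bedside nurse around each daily dose. Section 1.4(f) names COWS as the monitoring measure for the opioid-withdrawal risk of naloxegol.

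The scale is printed twice. Protocol Appendix 6 gives the published form and states "The total score is the sum of all 11 items". Its GI item runs "2 nausea or loose stool 3 vomiting or diarrhea 5 multiple episodes of diarrhea or vomiting", with 0 for no symptoms and 1 for stomach cramps. The severity key begins "Score: 5-12 = mild". The introduction to that form tells the rater to score signs only so far as they appear to come from withdrawal.

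Protocol Appendix 9 is the form the nurse completes. It carries the same GI points ("2 = nausea or loose stool 3 = vomiting or diarrhea 5 = multiple episodes of vomiting or diarrhea") and the same look-back ("GI Upset: Over Last ½ Hour"), with ratings 1 hour before and 2 hours after the dose. It does not repeat the general attribution instruction. It keeps item-level qualifiers for sweating, aches and runny nose, but has none for GI upset.

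Diarrhea is a separate safety outcome, section 2.3(a). Section 12.2 of the Protocol and of the SAP does not mention COWS, so no analysis method is stated for it and nothing sets the GI item apart.

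**The concern.** The trial tests a drug for its effect on the bowel, and one item of its withdrawal measure scores bowel activity. Patients without a bowel movement also move up a laxative ladder (Protocol Appendix 1), which can loosen stool in either arm. A change in the COWS total around a dose can therefore come from withdrawal, from the drug's peripheral bowel action, from a rescue laxative, or from the illness itself. The total does not show which.

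At stake is what the trial can say about withdrawal. The research hypothesis in section 1.3 includes safety, and the safety data go to the monitoring board by blinded group after 10 and 20 subjects. With 18 patients per arm, a few GI scores could create a between-arm difference that reads as withdrawal, or hide one that is withdrawal.

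**Working it through.** The plan gives no sample size, power or cut-off for COWS, so there is no stated figure to reproduce. The check works from the printed item points.

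**1. Maximum score.** Item maxima from Appendix 6: pulse 4, sweating 4, restlessness 5, pupils 5, aches 4, runny nose 4, GI upset 5, tremor 4, yawning 4, anxiety 4, gooseflesh 5.

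4 + 4 + 5 + 5 + 4 + 4 + 5 + 4 + 4 + 4 + 5 = 48. Without GI upset: 48 − 5 = 43, on 10 items.

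**2. Contribution to the outcome.** The GI part of the difference is (GI post-dose) − (GI pre-dose), and each rating is 0, 1, 2, 3 or 5.

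| GI pre-dose | GI post-dose | Contribution |
|---|---|---|
| 0 | 2 (loose stool) | +2 |
| 0 | 3 (diarrhea) | +3 |
| 0 | 5 (repeated episodes) | +5 |
| 2 | 2 | 0 |
| 3 | 0 | −3 |
| 5 | 0 | −5 |

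The range is −5 to +5. A formed stool without GI symptoms scores 0 and contributes nothing.

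**3. Relation to the printed mild band (5 to 12).** Non-GI points needed to reach 5 are 5 − (GI score).

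| GI score | Non-GI points needed |
|---|---|
| 2 | 3 |
| 3 | 2 (for example a pulse of 101 to 120) |
| 5 | 0 |

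Only the top GI score reaches the band by itself.

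**4. How much of the day the item sees.** With ratings 1 hour before and 2 hours after the dose and a half-hour look-back, the item covers 1.5 to 1 hours before the dose and 1.5 to 2 hours after it. That is 0.5 + 0.5 = 1 hour in 24.

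**5. Effect on a between-arm mean (assumed frequencies).** The documents give no frequency for new GI scores after a dose. If a fraction f of dose-days in one arm gains g points and the other arm gains none, the mean between-arm difference moves by f × g.

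| f (assumed) | g = 2 | g = 3 | g = 5 |
|---|---|---|---|
| 10% | 0.2 | 0.3 | 0.5 |
| 25% | 0.5 | 0.75 | 1.25 |
| 50% | 1.0 | 1.5 | 2.5 |

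The sign depends on which arm gains. If both arms gain equally, the shift is 0.

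**The case against.** The best case for leaving the plan alone has four parts. COWS is used as published, and GI upset is itself a sign of withdrawal, so removing it removes part of what is being measured. Appendix 6 already tells the rater to exclude findings that do not look like withdrawal. The half-hour look-back misses most stools, and section 5.8.1 holds study drug when excessive diarrhea occurs, so held days have no dose to rate around. Items are recorded one by one, so anyone with the data can inspect the GI item later.

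Much of this stands. It is why the total should stay and why the point is small. Three things remain. The attribution instruction is missing from the form nurses fill in, and even with it a blinded nurse has no stated way to tell laxation from withdrawal. A single loose stool triggers no hold yet scores 2. Finally, a comparison chosen after seeing the data carries less weight than one named in advance.

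A reader might also infer that naloxegol's intended effect alone would register as mild withdrawal, with a bias always against naloxegol. The documents do not support that:

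- Under section 2.1 the intended effect is any spontaneous rectal output, with no looseness required. Loose stool (2) and diarrhea (3) each stay below 5.
- No cut-off is part of outcome 2.3(d). The severity bands are only text on the forms.
- Direction is not fixed. Equal ratings cancel, and loose stool present only before the dose lowers the difference. If naloxegol works, placebo patients may receive more rescue laxatives. The item also scores nausea and vomiting, which section 1.1 attributes to lower GI tract paralysis.

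Nor do the documents show diarrhea counted twice as harm. Outcomes 2.3(a) and 2.3(d) use different windows (24 hours and half an hour), and no composite adds them.

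**Conclusion.** The point holds as a modest improvement to a safety analysis. Total COWS mixes GI effect with withdrawal, by up to 5 of 48 points in either direction on any pre/post pair, and no passage of the Protocol or SAP separates the two. How often this would happen, and which arm it would favor, cannot be read from the documents. The 0.2 to 2.5 point shifts in the mean rest on assumed frequencies of 10% to 50% in one arm and none in the other. They show scale only and are not a prediction. The primary outcome is unaffected.

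**What to change.** Keep total COWS as outcome 2.3(d). Prespecify in section 12.2 the same pre/post between-arm comparison with the GI item removed (10 items, maximum 43), report the two side by side, and base any statement about withdrawal on both. Because section 12.2 names no method for COWS, the method has to be stated once and applied to both scores. Repeat the Appendix 6 attribution instruction on the Appendix 9 nurse form.

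The cost is one extra analysis and one added line on a form. No new data are needed, since Appendix 9 already records each item. The drawbacks are that the 10-item score has no severity bands of its own and omits an item that can reflect true withdrawal. It therefore supplements the total and does not replace it.
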